## **10.0 SUBJECT DEATH**

### **10.1.1 Procedure for recording and reporting subject death**

All subject deaths will be collected throughout the clinical study and will be recorded on a dedicated case report form.

## **11.0 DATA MANAGEMENT**

The investigative team will manage the data. The investigative team will capture the data in the RedCap database provided by the university. RedCap is a secure method of capturing and storing the data.

The Sponsor/Investigator will be responsible for compiling and submitting all required reports to governmental agencies.

The privacy of each subject and confidentiality of his/her information will be preserved in reports and when publishing any data. Confidentiality of data will be observed by all parties involved at all times throughout the clinical study. All data will be secured against unauthorized access.

### **11.1 DOCUMENT AND DATA CONTROL**

#### **11.1.1 Traceability of documents and data**

The investigator will ensure accuracy, completeness, legibility, and timeliness of the data reported on the CRFs and in all required reports.

#### **11.1.2 Recording data**

Source documents will be created and maintained by the investigational site team throughout the clinical study.

The data reported on the CRFs will be derived from, and be consistent with, these source documents, and any discrepancies will be explained in writing.

## 12.0 MONITORING

Monitoring will occur through routine internal data review. This monitoring is designed to identify missing and inconsistent data, data outliers, and potential protocol deviations that may be indicative of non-compliance.

## 13.0 REGULATORY INSPECTIONS

An investigator who has authority to grant access will permit authorized governmental agency employees, at reasonable times and in reasonable manner, to enter and inspect any establishment where drugs are held (including any establishment where drugs are used or where records or results are kept).

An investigator, or any person acting on behalf of such a person with respect to the study, will permit authorized governmental agency employees, at reasonable times and in reasonable manner, to inspect and copy all records relating to the study.

An investigator will permit authorized governmental agency employees to inspect and copy records that identify subjects, upon notice that governmental agency has reason to suspect that adequate informed consent was not obtained, or that reports required to be submitted by the investigator have not been submitted or are incomplete, inaccurate, false or misleading.

## 14.0 STATISTICAL CONSIDERATIONS

### 14.1 STATISTICAL DESIGN, HYPOTHESES, METHOD AND ANALYTICAL PROCEDURES

This clinical study will provide data to support the safety, preliminary efficacy, and performance of the use of the Amiodarone hydrogel in preventing atrial arrhythmia during lung transplantation. The study has a treatment arm and a control arm. The control arm is the historic controls and will use the previously treated lung transplant patients at the facility. The treatment arm will use investigational amiodarone hydrogel. The study sample size calculation is based on typical regulatory criteria for a feasibility study to assess for safety and preliminary effectiveness hence it is not based on a power analysis to show statistically significant difference between the groups. However, the reported rate of early atrial fibrillation post lung transplantation is approximately 30% and assuming that the use of amiodarone gel will result in prevention of atrial fibrillation in 90% patients a sample size of 20 in each arm may have sufficient power to answer the question of preliminary effectiveness and safety.

Endpoint analysis will be on “as-treated” basis as historical control data will be used. Patients who will dropout or withdraw from the study before reaching the primary end-point will be excluded from the study and replaced by new enrollees to have at least 20 patients enrolled the study arm. The primary end-point analysis will be based on the study groups as per the protocol (treatment group vs. control groups). Subjects, who withdraw consent, will not be included in analyses.

All clinically relevant baseline and follow up variables will be tabulated. Means, medians, proportions and 95% confidence intervals will be reported. Comparisons of data collected at baseline and at follow-up will be analyzed as follows: categorical variables will be tested using contingency tables analyses (exact or chi-square approximations), and continuous variables will be tested using unpaired Student’s t-test or Wilcoxon rank-sum test, depending on variable distribution. The post-transplant AFIB was evaluated between study and control groups for overall occurrence, AFIB lasting < 24 hours and AFIB lasting > 24 hours. All the data were analyzed using SAS 9.4 software (SAS Inc., Cary, NC).

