## 2.0 BACKGROUND AND JUSTIFICATION FOR CLINICAL STUDY

Approximately 1900 transplants are performed in the US annually. Lung transplantation remains the gold standard treatment for patients with end stage lung disease. This includes patients with range of etiologies such as Idiopathic Pulmonary Fibrosis, COPD and Cystic Fibrosis. One of the more common post-operative complications in patients undergoing lung transplantation is the development of atrial fibrillation. Recent studies have demonstrated that approximately 1/3 of patients will develop atrial fibrillation during their post-operative course. While it is uncertain if the development of post-operative atrial fibrillation affects survival, it does significantly increase length of hospital stay. Importantly, a portion of the patients that develop atrial fibrillation post-operatively will require cardioversion prior to discharge.

Currently one of the main stays of treatment for post-operative atrial fibrillation is systemic (oral or intravenous) amiodarone, which is a class III antiarrhythmic agent. While this particular drug is effective, it does carry the risk of several known complications. Due to the drug's pharmacokinetics, amiodarone concentrates in organs with high lipid content such as the thyroid, liver and lung. Amiodarone has several known adverse effects on the lung ranging from acute respiratory distress syndrome to more chronic disease such as Interstitial pulmonary fibrosis. Amiodarone can have detrimental effects on the liver which in rare cases could lead to cirrhosis. Additionally, amiodarone can cause thyrotoxicosis as early as a few weeks after the initiation of amiodarone.

The adverse events listed above are related to the cumulative dose of amiodarone. Typically, when amiodarone is initiated, patients receive a loading dose of 600-800mg daily until the cumulative dose reaches 10 grams, after which patients will receive 200mg daily as a maintenance dose. Minimizing the cumulative dose of amiodarone by using a local application, could mitigate the potential adverse drug toxicities. In a previous study, the application of an amiodarone releasing hydrogel performed intraoperatively was shown to significantly decrease the rates of post-operative atrial fibrillation in patients undergoing coronary artery bypass. Currently for patients undergoing lung transplantation, there is not a safe and effective measure available to prevent post-operative atrial fibrillation.

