### **4.2 STUDY DESIGN AND SCOPE**

This study will prospectively evaluate the use of an amiodarone releasing hydrogel applied to the pulmonary veins and atria at the time of lung transplantation. This study will include patients undergoing lung transplantation at Jewish Hospital, Louisville KY. The prospective group will be compared to historical controls from the same institution. We will access medical records and database entries for those patients undergoing lung transplantation after January 1st 2005 in order to obtain matched controls for analysis. Informed consent will be obtained from the prospective cohort prior to patient enrollment. This pilot study will be used to obtain preliminary data in order to proceed with a larger randomized, controlled trial.

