#### **4.2.3 Number of subjects required to be included in the study**

Enrollment will include at least 20 patients undergoing lung transplant. The subjects will be evaluated with the historic controls (50).

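### The remark in Section 14.1 that 20 per arm may be sufficiently powered is not borne out by its own inputs, and 20 per arm is not the planned comparison

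*Combined protocol and SAP*

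**What the plan says.** Section 14.1 describes a feasibility size and says that "it is not based on a power analysis to show statistically significant difference between the groups". The next sentence qualifies this. It takes a reported early AF rate of about 30%, assumes "prevention of atrial fibrillation in 90% patients" with the gel, and concludes that "a sample size of 20 in each arm may have sufficient power to answer the question of preliminary effectiveness and safety". It gives no AF rate for the treated arm, no significance level, no sidedness, no target power and no computed power.

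The same section says that categorical variables will be compared by "contingency tables analyses (exact or chi-square approximations".

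Other sections bear on the claim:

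- Section 4.2.3 plans at least 20 treated patients, and on the comparator says "The subjects will be evaluated with the historic controls (50".
- Section 4.2 says that records from 2005 onwards will be searched "in order to obtain matched controls for analysis", and that "This pilot study will be used to obtain preliminary data in order to proceed with a larger randomized, controlled trial".
- Section 2.0 gives a slightly higher background rate: "approximately 1/3 of patients will develop atrial fibrillation during their post-operative course". Section 3.7 also uses one third.

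**The concern.** Although hedged, the sentence is a power claim with its own inputs, so it can be checked. It has three weaknesses.

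1. The assumed effect has two readings. If 90% of treated patients stay free of AF, the treated rate is 10%. If 90% of the expected AF is prevented, the treated rate is 0.1 × 30% = 3%. These are very different effects to detect with 20 patients.
2. On either reading, 20 per arm looks small for a between-group test at a conventional level.
3. The claim describes 20 versus 20, but the planned comparison is 20 versus 50.

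What is at stake is how the result is read. If the plan says that power may be sufficient, a non-significant AF comparison can be taken as evidence that the gel does not work, and that could weigh on the decision about the larger randomized trial. Whether a null result carries any information depends on which treated rate was meant, and the text leaves that open.

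**Working it through.** **Inputs from the documents.** Control AF rate 30% (14.1), or 1/3 as a sensitivity value (2.0, 3.7). Treated AF rate 10% or one tenth of the control rate (the two readings of 14.1). Treated patients 20; controls 20 (14.1) or 50 (4.2.3). Tests: exact or chi-square (14.1). Dropouts before the primary endpoint are replaced, so no inflation is needed.

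**Assumptions, not in the documents.** Two-sided 5% level, independent arms, and 80% as the conventional benchmark for sufficient power.

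**The plan's own figure.** Section 14.1 prints no power value, so only the conclusion that 20 per arm may suffice can be tested.

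**Step 1: normal approximation.** Let pC and pT be the control and treated rates, nC and nT the arm sizes, and p̄ = (nC·pC + nT·pT)/(nC + nT). Then

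power ≈ Φ{[(pC − pT) − 1.96·s0]/s1}, with s0 = √[p̄(1 − p̄)(1/nC + 1/nT)] and s1 = √[pC(1 − pC)/nC + pT(1 − pT)/nT].

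- 20/20, 30% vs 10%: p̄ = 0.200, s0 = 0.1265, s1 = 0.1225; (0.20 − 0.2479)/0.1225 = −0.391; power 34.8%.
- 20/20, 30% vs 3%: p̄ = 0.165, s0 = 0.1174, s1 = 0.1093; (0.27 − 0.2301)/0.1093 = 0.365; power 64.3%.
- 20/50, 30% vs 10%: p̄ = 17/70 = 0.243, s0 = 0.1135, s1 = 0.0933; power 40.5%.
- 20/50, 30% vs 3%: p̄ = 15.6/70 = 0.223, s0 = 0.1101, s1 = 0.0752; power 76.4%.

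**Step 2: exact power.** Sum the product of the two binomial probabilities over every pair of event counts for which the test rejects. Each cell runs from Fisher exact to the uncorrected test (chi-square if two-sided, z if one-sided).

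| Control vs gel AF rate | 20/20, two-sided 5% | 20/50, two-sided 5% | 20/20, one-sided 5% | 20/50, one-sided 5% |
|---|---|---|---|---|
| 30% vs 10% | 24-36% | 33-44% | 34-49% | 47-57% |
| 30% vs 3% | 56-71% | 71-83% | 64-82% | 84-91% |
| 1/3 vs 10% | 32-45% | 46-55% | 43-58% | 59-68% |
| 1/3 vs 3.3% | 64-77% | 80-88% | 72-86% | 90-94% |

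A continuity-corrected chi-square is lower still: at 20/20, two-sided 5%, it gives 22% for 30% vs 10% and 46% for 30% vs 3%.

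**Step 3: size needed.** For 80% power at 1:1, two-sided 5%, without continuity correction:

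n per arm = [1.96·√(2p̄(1 − p̄)) + 0.842·√(pC(1 − pC) + pT(1 − pT))]² / (pC − pT)².

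This gives 61.6, so 62 per arm, for 30% vs 10%, and 28.5, so 29 per arm, for 30% vs 3%. At one-sided 5% the figures are 49 and 23. None of these is 20.

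**Step 4: precision if the 10% reading came true exactly.** Observed 2/20 vs 15/50 gives Fisher p = 0.122 and uncorrected chi-square p = 0.078. The Wilson 95% limits are 0.028 to 0.301 and 0.191 to 0.438. The Newcombe interval for the difference is then

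- lower: −0.20 − √[(0.100 − 0.028)² + (0.438 − 0.300)²] = −0.355
- upper: −0.20 + √[(0.301 − 0.100)² + (0.300 − 0.191)²] = +0.029

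That is about −36 to +3 percentage points.

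**The case against.** The strongest defence is that nothing here is a failed calculation. The plan says outright that the size is not power-based, calls the study a pilot, and hedges the remark. It sets no alpha and no target, so the two-sided 5% level and the 80% benchmark are mine. A looser standard changes part of the picture. At one-sided 10%, the 3% reading at 20/20 has 79-91% power with a 30% control rate and 84-93% with one third. The 50 controls raise power in every scenario, and on the 3% reading the uncorrected chi-square reaches 83% even at two-sided 5%. No decision rule uses the p-value, and confidence intervals are promised, which would partly show the imprecision.

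Much of this stands. The remark is an unsupported aside, enrolment does not depend on it, and the 3% reading is defensible under favourable assumptions. The 10% reading is not defensible at 20 per arm: even at one-sided 10%, power is 48-71% over both tests and both control rates. With 50 controls at that level, the same enumeration passes 80% only with the one-third control rate and the uncorrected z test (84%). The section commits to between-group tests and offers no other criterion for sufficiency. For safety it states no hypothesis, so that half of the claim cannot be checked. The two meanings of 90% and the mismatch between 20 and 50 controls need no assumption about alpha.

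**Conclusion.** The concern holds. At an assumed two-sided 5% level with independent arms, 20 per arm falls short of 80% power on both readings, with either control rate and either kind of test that the plan allows.

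At one-sided 5%, the 10% reading still peaks at 58% with 20 controls and 68% with 50. At 20 per arm, 80% is then passed only on the relative-reduction reading with an uncorrected z test (82%, or 86% with a control rate of one third).

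For the comparison actually planned, the meaning of a null result turns on the undefined 90%. A true fall from 30% to 10% would more likely be missed than detected, whereas a true fall to 3% would more likely be detected. The practical consequence is modest because the study is openly a feasibility pilot, but the sentence should be corrected. The figures would change if the controls are analysed as matched sets.

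**What to change.** Delete the power remark in Section 14.1, or replace it with text such as:

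> This pilot was not sized to test efficacy. Assuming a two-sided 5% level and independent arms, 20 treated patients and 50 historical controls give 33% (Fisher exact) to 44% (uncorrected chi-square) power for 10% versus 30% AF, and 71% to 83% for 3% versus 30% AF. A non-significant result is not evidence of no effect.

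State which treated AF rate the 90% means, and keep only the matching figure. Reconcile the 20 controls implied in 14.1 with the 50 in 4.2.3. If the matched controls of 4.2 will be analysed as matched sets, say so, because the figures above assume independent arms.

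The cost is wording only: no extra patients and no change to the analysis. The plan's stated claim becomes less favourable.

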### **4.3 OBJECTIVES**

#### **4.3.1 Primary Objective**

Demonstrate safety and effectiveness of the amiodarone hydrogel application during lung transplantation in preventing atrial arrhythmias during index hospital stay.

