### **4.4. ENDPOINTS**

#### **4.4.1 Primary Endpoint**

-Development of post-operative atrial fibrillation during initial hospitalization

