## 17.0 INVESTIGATION SUSPENSION OR TERMINATION

### 17.1 PREMATURE TERMINATION OF THE WHOLE CLINICAL STUDY

The Sponsor/Investigator reserves the right to stop the study at any stage, with appropriate written notice.

Possible reasons for early termination of the study by the investigator may include, but are not limited to:

- The drug/therapy fails to perform as intended
- Occurrence of USADE which cannot be prevented in future cases
- Request from Regulatory bodies
- Concern for subject safety and welfare
- Failure to secure subject Informed Consent prior to any investigational activity
- Failure to report unanticipated adverse drug effects to IRB
- Inability to successfully implement this CIP
- Violation of the Declaration of Helsinki 2008 (refer to Appendix C)
- Violation of applicable national or local laws and regulations

The study will be terminated according to applicable regulations.

If suspicion of an unacceptable risk to subjects arises during the clinical study or when so instructed by the IRB or regulatory authority, the study may be suspended as appropriate while the risk is assessed. The Sponsor/Investigator will terminate the clinical study if an unacceptable risk is confirmed.

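### Section 14.1 suggests 20 per arm may have sufficient power for preliminary effectiveness; on its own assumptions power at two-sided 5% is 24% to 71% with 20 controls, and no criterion is stated

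*Combined protocol and SAP*

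**What the plan says.** The primary endpoint (section 4.4.1) is binary: "Development of post-operative atrial fibrillation during initial hospitalization". The primary objective in section 4.3.1 is worded as a demonstration: "Demonstrate safety and effectiveness of the amiodarone hydrogel application during lung transplantation in preventing atrial arrhythmias during index hospital stay". Section 4.2 places the study before a further one: "This pilot study will be used to obtain preliminary data in order to proceed with a larger randomized, controlled trial".

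Section 14.1 says the size follows feasibility-study practice and was not derived from a power analysis for a significant difference. It then offers a power-type justification. It says that "the reported rate of early atrial fibrillation post lung transplantation is approximately 30" per cent, continues "assuming that the use of amiodarone gel will result in prevention of atrial fibrillation in 90% patients", and concludes that "a sample size of 20 in each arm may have sufficient power to answer the question of preliminary effectiveness and safety".

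For analysis, section 14.1 says "categorical variables will be tested using contingency tables analyses (exact or chi-square approximations" are to be used, and that proportions and 95% confidence intervals will be reported. It states no hypothesis, alpha, sidedness, power value or interval method, and does not say what AF result would count as preliminary effectiveness. It speaks of 20 in each arm, whereas section 4.2.3 sets at least 20 treated patients against 50 historical controls.

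**The concern.** The two statements in 14.1 pull against each other. The first disclaims power; the second tells the reader that the size may be adequate to answer the effectiveness question. The second can be checked against the rates beside it, and it does not hold at a conventional level on the literal reading of those rates.

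Nor can the question be answered as posed, because the plan does not say what an answer looks like. Exact or chi-square, one- or two-sided, 20 or 50 controls, and the interval method are all left open. In a study this small those choices change the reading of the same data. The study is open-label and run by a sponsor-investigator, so they could be made after the AF counts are known. At stake is whether the pilot's AF result is reported as support for the gel on grounds fixed beforehand.

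**Working it through.** **Inputs.** Control AF 30% (14.1). Gel AF: 10% if 90% of treated patients are AF-free (literal reading), or 30% × (1 − 0.90) = 3% if 90% is a relative reduction. Treated n = 20. Controls 20 (14.1) or 50 (4.2.3). Alpha is not stated; two-sided 5% is assumed, with one-sided 5% as a sensitivity case. Groups are treated as independent, although 4.2 calls the controls matched, because the test in 14.1 is unmatched.

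**Step 1: the plan's figure.** There is no stated power to reproduce, so I asked what standard target would give 20 per arm:

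n = [z(1−α/2)·√(2p̄q̄) + z(1−β)·√(p₁q₁ + p₂q₂)]² / (p₁ − p₂)²

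- 10% v 30%, 80% power: [1.960 × √0.32 + 0.842 × √0.30]² / 0.04 = 2.464 / 0.04 = 61.6, so 62 per arm (82 for 90% power). One-sided 5%: 49 and 67.
- 3% v 30%, 80% power: 29 per arm (38 for 90%). One-sided 5%: 23 and 31.

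None of these gives 20; a continuity correction raises them all.

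**Step 2: exact power.** Sum Binomial(20, p gel) × Binomial(m, 0.30) over all outcomes where the test rejects. Entries are Fisher / uncorrected chi-square.

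| Gel AF | Level | 20 v 20 | 20 v 50 |
|---|---|---|---|
| 10% | two-sided 5% | 24% / 36% | 33% / 44% |
| 10% | one-sided 5% | 34% / 49% | 47% / 57% |
| 3% | two-sided 5% | 56% / 71% | 71% / 83% |
| 3% | one-sided 5% | 64% / 82% | 84% / 91% |

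At the 20 v 20 size named in 14.1, power reaches 80% only with the 3% reading, a one-sided test and uncorrected chi-square together.

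**Step 3: the hoped-for result, if observed exactly (10% v 30%).** z = (p_C − p_G) / √[p̄q̄(1/n_G + 1/n_C)].

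- 2/20 v 15/50: p̄ = 17/70 = 0.243; z = 0.20 / √(0.243 × 0.757 × 0.07) = 1.763. Two-sided p = 0.078 (chi-square), 0.122 (Fisher). One-sided p = 0.039 and 0.068.
- 2/20 v 6/20: p̄ = 8/40 = 0.20; z = 0.20 / √(0.16 × 0.10) = 1.581. Two-sided p = 0.114 and 0.235.

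95% CI for the 20-point difference:

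- 20 v 50, Wald: 0.20 ± 1.96 × √(0.09/20 + 0.21/50) = 1.7 to 38.3 points, excluding zero.
- 20 v 50, Newcombe: −2.9 to 35.5 points, including zero.
- 20 v 20: −4.0 to 44.0 (Wald) and −5.4 to 43.1 (Newcombe), both including zero.

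So for 2/20 v 15/50 the unstated sidedness, test and interval method decide whether the result looks positive.

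**Step 4: one possible criterion.** Take as a rule that the upper one-sided 90% score bound for the risk difference (gel minus control) lies below 0. By the same enumeration:

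| Design | Passes if gel has no effect (30%) | Passes if gel AF is 10% |
|---|---|---|
| 20 v 50 | 11% | 76% |
| 20 v 20 | 11% | 63% |

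The 11% requires the historical AF rate to equal today's untreated rate. If historical AF were 35% or 40% with a current untreated rate of 30% (assumed drifts), the false-pass rate at 20 v 50 would be 20% or 32%.

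**The case against.** The strongest reply is that this is a declared feasibility study. Section 14.1 disclaims power, hedges with the word may, and commits to proportions with 95% intervals, which is a legitimate pilot output. The Synopsis words its primary objective as evaluation. All of that stands: a non-significant 10% v 30% would be consistent with the plan, and lack of power is not in itself an error. The reply does not rescue the power sentence, which says more than the disclaimer allows and fails on the rates it cites.

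Four stronger readings are tempting, and the documents do not support them.

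- *The pilot decides whether a randomized trial goes ahead, so it lacks an essential go rule.* Section 4.2 presents the data as a step towards that trial; it does not make the trial conditional on the AF result. Without such a role, the absent rule is missing detail.
- *A gel that works as assumed would more likely than not fail.* This holds on the 10% reading at two-sided 5%. On the 3% reading with 50 controls, power is 71% or 83%.
- *The contingency-table test is the plan's decision tool.* Section 14.1 never calls it that, and it sits beside interval estimates.
- *Section 17.1 should share the criterion, since it lists "The drug/therapy fails to perform as intended".* Section 17.1 concerns premature termination. A criterion applied after every index stay is complete cannot govern that.

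**Conclusion.** The concern holds as a defect in 14.1's justification and in its specification of the primary comparison. The suggestion of sufficient power is unsupported on the literal rates: 24% to 44% at two-sided 5% across both tests and both control numbers. On the more favourable 3% reading it is still only 56% or 71% at the 20 per arm that the sentence names; the 83% figure needs 50 controls and chi-square.

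These figures rest on an assumed 5% level, independent groups and a true control rate of 30%. They do not show that the study is too small for a pilot. They show that the sentence should not stand, and that the test, sidedness, interval method and control number need fixing beforehand because they can reverse the reading of 2/20 v 15/50. Which numerical cut-off to adopt, if any, is a trade-off on which statisticians would reasonably differ.

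**What to change.** In section 14.1:

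1. Delete the sentence on sufficient power.
2. Reconcile the control number (20 in 14.1, 50 in 4.2.3) and state whether the 90% figure implies 10% or 3% AF on gel.
3. Give the actual power or expected interval width for that design, noting that it assumes the historical AF rate equals the current untreated rate.
4. Before any outcome data are seen, name one test, its sidedness and one CI method for the primary AF comparison.
5. State the basis for interpretation, for example: *Preliminary effectiveness will be judged from the AF risk difference (gel minus control) with its 95% confidence interval, by the named method; the result is not confirmatory.*

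If the sponsor wants a numerical criterion, the one-sided 90% score bound is one option. Its pass rates should be quoted for the reconciled design, with the historical-drift caveat beside them. It would address AF only, so safety would still need its own judgement.

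The cost is a few sentences in 14.1 and an aligned figure in 4.2.3, with no added patients, visits or data. The sponsor gives up the statement that the size may be adequate and the freedom to choose the analysis after seeing the counts.
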